7.3.2 Secondary analyses

In dose finding part, number of patients with OR will be described per dose level.

Proprietary confidential information.

© 2017 Boehringer Ingelheim International GmbH or one or more of its affiliated companies. All rights reserved.

This document may not - in full or in part - be passed on, reproduced, published or otherwise used without prior written permission.

In the MTD expansion cohorts/Phase II part, the PFS and DoR will be secondary endpoints. PFS is defined as the time from the date of first administration of treatment to the date of disease progression, or to the date of death, whichever comes first. The Kaplan-Meier estimates of PFS rate and 95% confidence intervals will be calculated at the time of each planned assessment. DoR is defined only for those patients with a response (CR or PR) as the interval between the date of randomization and the earliest date of disease progression. The Kaplan-Meier estimates of DoR and 95% confidence intervals will be calculated at the time of each planned assessment.

Pharmacokinetics is a secondary endpoint for the MTD expansion cohorts/Phase II part. For details see [Section 7.3.5](#).

7.3.3 Safety analyses

DLTs will be tabulated for each dose cohort in the Phase I dose finding part. The tabulation will be done in two ways: (1) DLTs with onset in the first treatment course; (2) all DLTs regardless of treatment course at onset. The definition of DLT is defined in [Table 4.1.4.1:2](#).

Events that started within the course of treatment, starting after the first administration of the treatment and until 28 days after the last administration of treatment will be considered as having occurred on treatment. In general later events will be attributed to the post-study period and will be presented separately. However post-study events will be examined to determine whether they need to be combined with on-treatment events in an additional table.

Adverse events will be graded according to CTCAE v3.0 and reported according to BI standards. Serious adverse events will be tabulated. In addition, events leading to dose reduction or treatment discontinuation will be examined, but may not be reported as individual tables, depending upon the extent of overlap.

Descriptive statistics will be used to describe changes in laboratory parameters over time. In addition, all abnormalities of potential clinical significance will be reported. In general, potential clinical significance is defined as at least CTCAE Grade 2 and an increase in

Proprietary confidential information.

© 2017 Boehringer Ingelheim International GmbH or one or more of its affiliated companies. All rights reserved.

This document may not - in full or in part - be passed on, reproduced, published or otherwise used without prior written permission.

CTCAE classification from baseline. The incidence and intensity of adverse events will be correlated descriptively with pharmacokinetic data if possible.

7.3.4 Interim analyses

No formal interim analysis is planned.

Results of the dose finding part and PK may need to be summarized and documented.

7.3.5 Pharmacokinetic analyses

Extensive plasma sampling:

Pharmacokinetic profiles of afatinib will be taken on Day 1 (after single dose) and Day 8 (at steady state) of Course 1. An additional trough sample will be taken on day 15 to confirm steady state exposure to afatinib. If data allow, the following pharmacokinetic parameters will be evaluated:

- area under the plasma concentration-time curve
 - over the dosing interval τ (24 h) and after uniform intervals τ , following the first dose and at steady state (AUC_{0-24} and $AUC_{\tau,ss}$)
 - over the time interval from zero to the time of the last quantifiable drug concentration (AUC_{0-tz} and $AUC_{0-tz,ss}$) within the dosing interval τ
- maximum measured plasma concentration following the first dose and at steady state after uniform intervals τ (C_{max} and $C_{max,ss}$)
- time from dosing to the maximum plasma concentration following the first dose and at steady state after uniform intervals τ (t_{max} and $t_{max,ss}$)
- accumulation ratio ($R_{A,Cmax}$ and $R_{A,AUC}$)
- accumulation (or effective) half-life

Other parameters may be calculated as deemed appropriate.

The derivation of the PK parameters will be performed in line with BI internal procedures (MCS-36-472, current version). The accumulation (or effective) half-life can be calculated according to the formula $t_{1/2} = \tau \cdot \ln 2 / \ln(R_{A,AUC} / (R_{A,AUC} - 1))$ ([P09-09363](#)).

The following descriptive statistics will be calculated for all PK parameters: N, arithmetic mean, standard deviation, minimum, median, maximum, arithmetic coefficient of variation, geometric mean, and geometric coefficient of variation. The descriptive statistics of PK parameters will be calculated using the individual values with the number of decimal places as provided by the evaluation program. Then the individual values as well as the descriptive statistics will be reported with three significant digits in the clinical trial report.

Proprietary confidential information.

© 2017 Boehringer Ingelheim International GmbH or one or more of its affiliated companies. All rights reserved.

This document may not - in full or in part - be passed on, reproduced, published or otherwise used without prior written permission.

Sparse plasma sampling:

In the clinical trial report, afatinib plasma concentrations from patients who were not able to undergo extensive sampling, and for whom sparse sampling was performed, will be summarised by time point by descriptive statistics and, if feasible, graphically inspected.

Model based analysis

A model-based analysis over all available PK data (extensive and sparse sampling) will be performed.

Structure of the available population PK model

Based on existing afatinib PK models in adult patients having various solid tumours (studies 1200.1; .2; .3; .4 and 20 ([U12-1393](#)) and 1200.28; .32 and .33 ([U12-1394](#))), a model will be developed based on 1200.120 data in paediatric population.

Model development

A non-linear mixed effect modelling approach will be taken to conduct the analysis. The parameters of the model are defined by fixed effects, so called θ s and potential random effects (Inter (η) or intra-individual variabilities (κ)). These random effects are normally distributed around zero with a variance ω^2 . The combination of the fixed effects and random effects allow the estimation of individual parameters (P_i) as described in the following example equation:

$$P_i = \theta * \exp(\eta_i)$$

In addition, a residual variability, ε , adjusts the prediction of the model to the observed measurement. This residual variability is normally distributed with a variance σ^2 and can be described according to the following equation:

$$Y_{i,j} = \text{IPRED}_{i,j} + \varepsilon_{i,j}$$

where $Y_{i,j}$ is the j^{th} observation for i^{th} individual, $\text{IPRED}_{i,j}$ is the individual prediction of the model for the j^{th} observation of the i^{th} individual, $\varepsilon_{i,j}$ is the residual variability for the j^{th} observation of the i^{th} individual. In the current situation Y is the plasma concentration of afatinib. If possible First Order Conditional Estimation with Interaction (FOCE / INT) will be used for the complete model development. The data from all dose groups of this study will be used for model development.

Effect on Body weight on clearance and on volume of distribution will be evaluated, and the respective parameters (CL, V) will be scaled based on body weight.

Handling of missing data: Samples marked as no sample available (NOS) or non-valid result (NOR) will not be included in the dataset. Handling of missing PK data will be performed according to BI standards as stated in [Section 7.4](#) (MCS-36-472, current version).

Proprietary confidential information.

© 2017 Boehringer Ingelheim International GmbH or one or more of its affiliated companies. All rights reserved.

This document may not - in full or in part - be passed on, reproduced, published or otherwise used without prior written permission.

The objective function value as well as the following criteria will be used to evaluate a model:

- A “successful minimization” statement by the NONMEM program at the end of the estimation step.
- The final parameter estimates have a number of significant digits ≥ 3 .
- Estimates of θ 's not close to a boundary.
- Correlation of the uncertainty of the estimates of fixed effect parameters < 0.95 and > -0.95
- No significant trends in the basic goodness-of-fit plots (predictions (PRED), individual predictions (IPRED) vs. dependent variable (DV))
- Residuals (weighted and un-weighted) scatter randomly and uniformly around zero when plotted against PRED, IPRED and TIME.
- Symmetric distributions of individual η s.

Results

The following outcomes of the modeling based analysis will be reported:

- Structure and parameter estimates of the final PK model including the potential covariate submodel.
- Steady state concentrations for appropriate age range will be simulated. $C_{\max,ss}$ and $AUC_{\tau,ss}$ as well as apparent clearance (CL/F) and volume of distribution (Vd/F) will be calculated from these predictions.

Further details will be described in the TSAP.

PK data (plasma and CSF) may additionally be used to evaluate the penetration of afatinib into the brain, applying non-compartmental methods and pharmacokinetic modelling techniques as appropriate.

7.3.6 Pharmacodynamic analyses

No formal pharmacodynamics analysis is planned.

7.3.7 Pharmacogenomic analyses

No pharmacogenomic analyses are planned.

7.3.8 Biomarker Analyses

The prevalence of biomarkers will be determined during the biomarker prevalence study taking place outside of the clinical trial but being informative for the latter.

7.4 HANDLING OF MISSING DATA

In general, missing data will not be imputed.

Proprietary confidential information.

© 2017 Boehringer Ingelheim International GmbH or one or more of its affiliated companies. All rights reserved.

This document may not - in full or in part - be passed on, reproduced, published or otherwise used without prior written permission.

- Missing or incomplete AE onset and end dates are imputed according to BI standards (001-MCG-156_RD-01)
- For pharmacokinetics:

Handling of missing PK data will be performed according to BI standards (MCS-36-472, current version). For the non-compartmental analysis, concentration data identified with NOS, NOR or NOA will generally not be considered. Concentration values in the lag phase identified as BLQ or NOP will be set to zero. All other BLQ/NOP values of the profile will be ignored. The lag phase is defined as the period between time zero and the first time point with a concentration above the quantification limit.

7.5 RANDOMISATION

No randomisation will be performed.

7.6 DETERMINATION OF SAMPLE SIZE

In order to complete the dose finding part, which uses a rolling 6 design (see [Table 4.1.4.1:1](#)) an estimated 24 evaluable patients will be needed given the number of dose levels to be tested in this trial. To further account for early drop-out of patients or patients not evaluable for DLT during the first course of treatment, an estimated 30 patients were planned to be recruited to achieve this. 17 patients were needed to determine the MTD ([c09990672-01](#)).

Once the MTD is determined, a minimum of 5 patients in each of the four following cohorts, i.e. HGG, DIPG, EM and a mixed histology agnostic cohort of patients with refractory tumours, (see [Section 3.3.2](#)) will be accrued into an MTD expansion cohorts/Phase II part ([Table 7.6:1](#)) to confirm a safe recommended Phase II dose (RPIID) and to be assessed for response. An exploratory cohort of patients with proven genomic, transcriptomic or proteomic alterations which are not defined in [Tables 5.6:1-5.6:4](#) will also be included. [Table 7.6:1](#) shows the probability of observing more than one responder given the total number of patients assuming the true response rate being 20% and 30% respectively.

Table 7.6:1 Probability of observing more than one responder for different response rates

Sample size per cohort		P(no response)*	P(1 or more response)**	P(2 or more response)***
ORR = 20%	5	32.8%	67.2%	26.2%
ORR = 30%	5	16.8%	83.2%	47.1%
ORR = 20%	6	26.2%	73.8%	34.4%
ORR = 30%	6	11.8%	88.3%	60%
ORR = 20%	10	10.7%	89.2%	62.4%
ORR = 30%	10	2.8%	97.2%	85.1%

*P(no response) = Chances of observing no response given the assumed response rate

**P(1 or more response) = Chances of observing one or more than one response given the assumed response rate

***P(2 or more response) = Chances of observing two or more than one response given the assumed response rate

Proprietary confidential information.

© 2017 Boehringer Ingelheim International GmbH or one or more of its affiliated companies. All rights reserved.

This document may not - in full or in part - be passed on, reproduced, published or otherwise used without prior written permission.

[Table 7.6:2](#) summarizes for different prevalences the adjusted number of patients needed to be screened to ensure for a certain number N of biomarker positive patients with a probability of 90%.

Table 7.6:2 Number of patients to be screened to have with 90% probability at least N biomarker positive patients

Number N of biomarker positive patients	Prevalence of biomarker positive patients (%)							
	5	10	15	20	25	30	35	40
20	529	263	174	130	103	85	72	63
30	754	375	249	185	147	122	104	90
40	975	485	322	240	191	158	135	117
50	1193	594	394	294	234	194	166	144
60	1410	702	466	348	277	230	196	171
70	1626	810	538	402	320	266	227	198
80	1840	917	609	455	363	301	257	224
90	2054	1023	680	508	405	336	287	250
100	2266	1130	751	561	447	372	317	277
200	4370	2180	1450	1085	866	720	615	537

Considering that up to 55 patients will be included into this trial and of these up to 38 will be selected by biomarkers as described earlier (See [Section 5.6](#)) into the MTD expansion/Phase II part and assuming a biomarker prevalence of 10-15%, between 322 - 485 patients will need to be screened for that biomarker.

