- 2. MTD expansion cohorts/Phase II part:** Once the MTD is determined, patients will be tested and recruited only if they fulfil at least two of the following biomarker criteria (i) EGFR gene amplification (FISH) *and/or* (ii) HER2 gene amplification (DDISH) *and/or* (iii) EGFR protein expression (membrane staining): H-score > 150 *and/or* (iv) HER2 protein expression (membrane staining): H-score > 0 ([see section 5.6](#)). A minimum of 5 patients in each of the four following cohorts, i.e. HGG, DIPG, EM and a mixed histology agnostic cohort of patients with refractory tumours, will be accrued to confirm a safe recommended Phase II dose (RPIID) and to be assessed for response. An exploratory cohort of a maximum of 6 patients with proven genomic, transcriptomic or proteomic ErbB alterations which are not defined above will also be included. This part of the trial will allow the collection of further safety and PK data to limit failure due to dosing issues in further clinical development, but also give insight if the "targeted" patient selection increases the level of clinical efficacy.

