7.2 NULL AND ALTERNATIVE HYPOTHESES

No formal hypothesis testing is planned in this trial. All analyses will be descriptive and exploratory in nature.

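### Protocol Table 7.6:1 gives a 60% chance of two or more responses in a cohort of 6 at a 30% response rate; the exact value is 58.0% (minor erratum)

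*Protocol*

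**What the plan says.** Protocol Section 7.6 introduces Table 7.6:1 as showing the chance of seeing more than one responder, "assuming the true response rate being 20% and 30% respectively". The title is "Probability of observing more than one responder for different response rates". The table covers cohort sizes of 5, 6 and 10 and has three probability columns, each defined in a footnote:

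- first column: "Chances of observing no response given the assumed response rate"
- second column: "Chances of observing one or more than one response given the assumed response rate"
- third column: "Chances of observing two or more than one response given the assumed response rate"

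The row at issue reads "ORR = 30% 6 11.8% 88.3% 60", where the last figure is a percentage. It therefore gives 60% for two or more responses among 6 patients at a 30% response rate.

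Section 3.1 shows where a size of 6 occurs in the design: "An exploratory cohort of a maximum of 6 patients" with other ErbB alterations. The four main cohorts have a minimum of 5. Section 7.2 says that "No formal hypothesis testing is planned in this trial".

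**The concern.** Each entry is a binomial probability that can be checked exactly, and one of them fails. It is also the only probability printed without a decimal. The table is the documents' statement of what a cohort of a given size can be expected to show about response; Table 7.6:2, the other table in the section, deals only with screening numbers. A reader weighing the exploratory cohort at its full size would find the chance of at least two responses slightly overstated.

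The SAP does not repair this. Its introduction refers readers to the protocol for the planning of sample size. Its Section 4 (changes in the planned analysis) corrects the definition of duration of response but does not mention this table.

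**Working it through.** **Inputs**, all from Protocol Section 7.6: response rates p = 0.20 and 0.30; cohort sizes n = 5, 6 and 10; column definitions from the footnotes.

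**Formulas**, for X ~ Binomial(n, p):

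- P(X = 0) = (1 - p)^n
- P(X ≥ 1) = 1 - (1 - p)^n
- P(X ≥ 2) = 1 - (1 - p)^n - n p (1 - p)^(n-1)

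**The cell in question**, n = 6, p = 0.30:

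- P(X = 0) = 0.7^6 = 0.117649
- P(X = 1) = 6 × 0.3 × 0.7^5 = 6 × 0.3 × 0.16807 = 0.302526
- P(X ≥ 2) = 1 - 0.117649 - 0.302526 = 0.579825, or 58.0%
- Printed: 60%. Difference: 60 - 57.98 = 2.02 points.

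**All 18 cells**, printed / exact, in percent:

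| n | p | none | 1 or more | 2 or more |
|---|---|---|---|---|
| 5 | 20% | 32.8 / 32.77 | 67.2 / 67.23 | **26.2 / 26.27** |
| 5 | 30% | 16.8 / 16.81 | 83.2 / 83.19 | **47.1 / 47.18** |
| 6 | 20% | 26.2 / 26.21 | 73.8 / 73.79 | **34.4 / 34.46** |
| 6 | 30% | 11.8 / 11.76 | **88.3 / 88.24** | **60 / 57.98** |
| 10 | 20% | 10.7 / 10.74 | **89.2 / 89.26** | 62.4 / 62.42 |
| 10 | 30% | 2.8 / 2.82 | 97.2 / 97.18 | 85.1 / 85.07 |

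Bold cells are wrong at the table's own precision of one decimal. Apart from the 60% cell, every entry is within 0.1 point of the exact value, so the method behind the table is not in doubt. Two of the last-digit slips show without recomputing anything, because the first two columns must sum to 100%: 11.8 + 88.3 = 100.1 and 10.7 + 89.2 = 99.9.

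**Could 60% come from another calculation?** Three or more responses in 6 gives 25.6%. Two or more in 7 patients gives 67.1%. A Poisson approximation with mean 6 × 0.3 = 1.8 gives 53.7%. None fits. At n = 6 the response rate would have to be about 31% (a rate of 0.31 gives 60.1%). Rounding 0.58 to one significant figure would give 60%, but no other cell is rounded that coarsely and the documents do not confirm it.

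**The case against.** The strongest reply is that nothing depends on the cell, and that stands. The analyses are descriptive. The protocol sets no responder count for going forward; it leaves the response rate to the judgement of paediatric oncology experts and regulators (Section 3.2). The primary analysis is the observed response proportion with an exact 95% interval in treated patients (Protocol 7.3.1, SAP 7.4.2) and does not use the table. The uncertainty in the assumed rate is also far larger than the error: for 6 patients the exact probability moves from 34.5% at a 20% rate to 58.0% at a 30% rate.

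Three stronger readings are tempting, and the documents do not support them.

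- *The title leads a reader to take 88% as the chance of more than one response.* More than one means two or more, which is the third column. A reader who follows the title reaches the 60% cell. The 88.3% stands under its own header and footnote for one or more. The title is incomplete, not wrong.
- *The table is optimistic throughout.* Only the 60% cell is materially high. Of the five last-digit slips, four understate the probability (26.2, 47.1, 34.4, 89.2). Only 88.3 overstates it, by less than 0.1 point.
- *The cohort sizes rest on the wrong figure.* No target probability is stated from which a size is derived. Section 2.3 ties the small number of patients per indication to the regulator's Written Request. Both rows for n = 5, the minimum of the main cohorts, are right to within 0.1 point.

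**Conclusion.** The cell is wrong. The probability of two or more responses in 6 patients at a 30% response rate is 58.0%, not 60%, an overstatement of 2.0 percentage points. Five further cells are wrong in the last digit, each by less than 0.1 point. The result assumes only that patients respond independently with a common probability, which is the model that the other 17 entries follow. The link to the exploratory cohort is through its maximum size in Section 3.1; Section 7.6 does not itself assign the row to that cohort.

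This is a minor correction to a stated operating characteristic. It changes no cohort size, analysis or conclusion.

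**What to change.** In Protocol Table 7.6:1, row ORR = 30% with n = 6, replace 60% by 58.0%. Correct five last digits:

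- two or more, n = 5, 20%: 26.2 to 26.3
- two or more, n = 5, 30%: 47.1 to 47.2
- two or more, n = 6, 20%: 34.4 to 34.5
- one or more, n = 6, 30%: 88.3 to 88.2
- one or more, n = 10, 20%: 89.2 to 89.3

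Optionally, widen the title and the introducing sentence to cover no, at least one and at least two responders.

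The cost is an editorial change to six cells and, if wished, one title and one sentence. The only substantive effect is that one figure becomes slightly less favourable.

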8. INFORMED CONSENT, DATA PROTECTION, TRIAL RECORDS

The trial will be carried out in compliance with the protocol, the principles laid down in the Declaration of Helsinki, in accordance with the ICH Harmonised Tripartite Guideline for Good Clinical Practice (GCP) and relevant BI Standard Operating Procedures (SOPs). Standard medical care (prophylactic, diagnostic and therapeutic procedures) remains in the responsibility of the treating physician of the patient.

The protocol has been written in compliance with the recommendations given by the ICH E 11 Guidance for Industry (Clinical Investigation of Medicinal Products in the Paediatric Population, [R10-4556](#)) and Ethical considerations for clinical trials on medicinal products conducted with the paediatric population ([R10-4959](#)).

The investigator should inform the sponsor immediately of any urgent safety measures taken to protect the study subjects against any immediate hazard, and also of any serious breaches of the protocol/ICH GCP.

Insurance Cover: The terms and conditions of the insurance cover are made available to the investigator and the patients via documentation in the ISF (Investigator Site File).

8.1 STUDY APPROVAL, PATIENT INFORMATION, AND INFORMED CONSENT

This trial will be initiated only after all required legal documentation has been reviewed and approved by the respective Institutional Review Board (IRB) / Independent Ethics Committee (IEC) and competent authority (CA) according to national and international regulations. The same applies for the implementation of changes introduced by amendments.

Prior to patient participation in the trial, written informed consent must be obtained from patient's parent(s) (both or one based on national regulation) or the legal guardian, as well as an informed assent of the minor patient according to ICH GCP and to the regulatory and legal requirements of the participating country. Each signature must be personally dated by each signatory and the informed consent and any additional patient-information form retained by the investigator as part of the trial records. A signed copy of the informed consent and any additional patient information must be given to each patient or the patient's legally accepted representative.

If only mother or father (or one legal guardian) has sole legal custody, this needs to be confirmed with signature and date on the informed consent by the person with legal custody. For the process of informed assenting, a separate patient information suitable for the respective age group will be provided to the patients. In the younger age group, children may not be capable of reading a text alone; in this case the parent(s) or legal guardian and/or site personnel need to read out the document.

Both documents (consent and assent) outline the participant's rights to decline to participate or to withdraw from the study at any time. Consenting/assenting is a dynamic and continuous process that should be maintained during the trial. At each new treatment course the site staff

Proprietary confidential information.

© 2017 Boehringer Ingelheim International GmbH or one or more of its affiliated companies. All rights reserved.

This document may not - in full or in part - be passed on, reproduced, published or otherwise used without prior written permission.

should briefly discuss with parents and patients the main aspects of the trial, focusing in particular on any new information that might affect their willingness to continue the participation in the trial. The site staff is recommended to document this process in the medical records.

The patient (where appropriate) and the patient's parent(s) or legal guardian must be informed that his/her personal trial-related data will be used by Boehringer Ingelheim in accordance with the local data protection law. The level of disclosure must also be explained to the patient and his/her parent(s) or legal guardian.

The patient (where appropriate) and the patient's parent(s) or legal guardian must be informed that his / her medical records may be examined by authorised monitors (CML/CRA) or Clinical Quality Assurance auditors appointed by Boehringer Ingelheim, by appropriate IRB / IEC members, and by inspectors from regulatory authorities.

